An age- and functional severity-matched (group-matching based on age and GMFCS level) control group, meeting the same inclusion criteria as the intervention group, but not receiving any intervention apart from their usual care, will be included. The participants of the control group will be recruited via Cerebral Palsy Reference Center of the University Hospitals Leuven, Belgium and the Inkendaal Rehabilitation Hospital Vlezenbeek, Belgium. All children eligible for inclusion will be measured, however the final data selection will be based on accurate matching with the participants in the intervention group. The participants in the control group will undergo 3DfUS measurements only, with an interval of 8-10 weeks between the two assessments.

Procedure

The most affected leg, based on the most recent clinical examination (highest modified Ashworth score for the ankle and knee joints), will be assessed. Measures of body mass, height, total leg length and lower leg length will be taken. A standardized anamnesis will be performed to request treatment history and usual care details.

Muscle selection for BoNT-A injection will be primarily based on the most recent clinical examination and multidisciplinary evaluation of the 3DGA data. BoNT-A, Onabotulinum toxin A (Botox®, Allergan) injections will be applied by a pediatric orthopedic surgeon under general (mask) anesthesia, guided by ultrasonography or palpation. A dose of 100 units of BoNT-A will be diluted in 5ml of saline. The BoNT-A dilution will be injected at multiple sites, in areas with the largest concentration of motor endplates in the muscles selected for treatment. A maximum of 50 units will be injected per site. BoNT-A is suggested to be more effective when part of an integrated approach, i.e., combined with casting, orthotic wear and physical therapy. Therefore, lower leg casts and removable upper leg casts will be applied as indicated.

All additional study assessments (3DfUS, clinical examination, instrumented spasticity assessment and 3DGA) will be performed by three trained assessors. The pre- and post-assessments will always be performed by the same assessor.

Assessments

1. Muscle morphology

Muscle morphology of the MG and distal compartment of the ST muscle will be assessed by 3DfUS. This technique, combining B-mode ultrasonography with three-dimensional motion tracking, is proven valid and reliable in muscle morphology assessments in children with SCP in previous studies.

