Gait cycles will be identified and manually marked using the Vicon Nexus software (Oxford Metrics, Oxford, UK). All trials will be exported and imported to a custom-made Matlab script (The MathWorks, Natick, MA, USA, 2020b). All gait cycles will be judged on quality. Trials will be excluded in case of artefacts, gaps in data or indications of inaccurate marker placement. Furthermore, the knee varus-valgus angle will be evaluated and trials with absolute knee varus-valgus ROM exceeding 15 degrees, a knee valgus angle exceeding -10 degrees, or trials that are not representative of the participants' gait pattern will be excluded. As many good-quality steps as possible, will be used to create average trials for the ankle and knee joint kinematics. The GPS, and specific kinematic gait parameters that are found to be sensitive to detect BoNT-A-induced changes, will be extracted per joint. Additionally, the spatial-temporal parameters cadence, walking velocity and stride length will be calculated. Finally the full kinematic waveforms will be exported for pre-post comparison.

The primary outcomes will include the kinematic waveforms, BoNT-A-sensitive kinematic gait parameters, GPS and spatial-temporal parameters.

3. Spasticity assessment

A subset of participants (n=14) will undergo an instrumented spasticity assessment in order to objectively evaluate the change in the hyperactive stretch reflex during passive stretch. This method has been previously described by Bar-On and colleagues and is proven sensitive enough to detect treatment-induced changes.

Four low-velocity (during 5 seconds) passive stretches of the plantar flexors and medial hamstrings will be performed over the full ROM. Next, four full ROM high-velocity passive stretches will be performed whereby the stretch will be performed as fast as possible. The interval between the stretch repetitions will be at least 7 seconds to avoid post-activation depression. During the stretches, muscle activation will be recorded by surface EMG (Zerowire Cometa, Milan, IT)

The raw EMG signals will be filtered by a 6th order zero-phase Butterworth bandpass filter (20-500 Hz) The root mean square envelope of the EMG signal (RMS-EMG) will be computed after application of a low-pass 30 Hz 6th order zero-phase Butter-worth filter.

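### Gait trials can be dropped as unrepresentative with no stated criterion and no stated masking to visit, so selection could bias the pre-post gait outcomes

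*Combined protocol and SAP*

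**What the plan says.** Section 2 (Gait analysis) describes the processing in this order.

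- Gait cycles are marked by hand, and then "All trials will be exported and imported to a custom-made Matlab script".
- "All gait cycles will be judged on quality". The text does not say who judges, or on which signal or curve.
- Technical exclusions: "Trials will be excluded in case of artefacts, gaps in data or indications of inaccurate marker placement".
- Numeric exclusions on the frontal-plane knee angle: "trials with absolute knee varus-valgus ROM exceeding 15 degrees, a knee valgus angle exceeding -10 degrees".
- In the same sentence, a last ground: "or trials that are not representative of the participants", completed by a reference to their gait pattern.
- "As many good-quality steps as possible, will be used to create average trials for the ankle and knee joint kinematics". No minimum or fixed number of steps is set.
- "The primary outcomes will include the kinematic waveforms, BoNT-A-sensitive kinematic gait parameters, GPS and spatial-temporal parameters".

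The Procedure section adds that "The pre- and post-assessments will always be performed by the same assessor". The Participants section limits the control group to ultrasound. Section 5 (Statistical Analysis) tests the gait measures within the treated children, pre versus post. A gait parameter counts as meaningful only if it is significant and also exceeds the SEM or MCID. A waveform cluster must last longer than 3% of the gait cycle and exceed the SEM. The SEM and MCID values are not given.

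**The concern.** The last ground for exclusion differs in kind from the others. Artefacts, gaps and marker faults are defects of measurement. The varus-valgus limits are numbers applied to an angle that is not among the sagittal ankle and knee motions tested. Whether a trial represents the child's gait pattern is a judgement about the quantity being studied, and the protocol supplies no definition, threshold, named or masked assessor, second rater, exclusion log or sensitivity analysis for it.

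If the person selecting trials knows the visit and expects improvement, a post-treatment trial that resembles the old pattern may look atypical, and so may an unusually good trial before treatment. A tendency that runs the same way across children does not average out. It would enter the mean change, which the analysis reads as an effect of treatment. With no gait data in controls, the planned analysis contains nothing that would reveal it. The Bonferroni correction limits chance findings among several parameters and does not act on bias.

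**Working it through.** **The plan's own figure.** The only computed figure that touches these outcomes is the Bonferroni level: 0.05/4 = 0.0125 (ankle) and 0.05/3 = 0.0167 (knee). Both reproduce. The documents give no figure for trial selection.

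**Inputs for the illustration.** None of these is in the documents: 10 steps per session; step-to-step SD 3 degrees; session-to-session SD 1.5 or 3 degrees; 14, 25 or 40 children; 1, 2 or 3 of 10 steps dropped per session; normal distributions; no true change. The SD of a child's pre-post change without exclusions is then √[2(1.5² + 3²/10)] = 2.5 degrees or √[2(3² + 3²/10)] = 4.4 degrees.

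**Size of a directional shift.** The expected three largest of 10 standard normal values are 1.539, 1.001 and 0.656. Dropping the top k moves the mean of the rest down by (sum of the top k)/(10 − k) SD. If the highest steps go at the first visit and the lowest at the second, the false change is twice that, times 3 degrees:

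- k = 1: 2 × 3 × 1.539/9 = 1.03 degrees
- k = 2: 2 × 3 × 2.540/8 = 1.91 degrees
- k = 3: 2 × 3 × 3.196/7 = 2.74 degrees

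The simulated means agree (about 1.0, 1.9 and 2.7). If only half the children are affected, the shifts halve, to about 0.5, 1.0 and 1.4 degrees.

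**Effect on the test.** Two-sided Wilcoxon signed rank test at 0.0125, 2000 simulated trials per setting (Monte Carlo standard error at the nominal level √(0.0125 × 0.9875/2000) = 0.0025). The ranges run over the assumed N and session SD.

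| Exclusion pattern | Steps dropped of 10 | Mean false change (degrees) | False-positive rate |
|---|---|---|---|
| None | 0 | 0.0 | 0.007–0.017 |
| Neutral: furthest from the session's own median | 1–3 | within 0.04 of 0 | 0.009–0.015 |
| Directional, every child | 1 | 1.0 | 0.03–0.47 |
| Directional, every child | 2 | 1.9 | 0.12–0.97 |
| Directional, every child | 3 | 2.7 | 0.29–1.00 |
| Directional, half the children | 1 | 0.5 | 0.02–0.10 |
| Directional, half the children | 2 | 1.0 | 0.03–0.34 |
| Directional, half the children | 3 | 1.4 | 0.06–0.63 |

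**A milder pattern.** Suppose the lowest fraction f of cycles is dropped at the second visit only. The shift is φ(z_f)/(1 − f): 0.195 SD for f = 0.10 and 0.350 SD for f = 0.20. With an assumed cycle SD of 4 degrees, that is 0.8 and 1.4 degrees. With an assumed SD of change of 4.5 degrees, the false-positive rate at 0.0125 is about 0.04 and 0.10 for 20 children, and about 0.05 and 0.17 for 30. A cycle SD of 2 degrees halves the shifts.

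**Reading.** Removing steps does not by itself cause bias; the removal must lean differently at the two visits. The neutral result also assumes symmetric step distributions. The rates describe the significance test alone. The added SEM or MCID requirement would lower the rate of declared meaningful changes, by an amount that cannot be computed without its values.

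**The case against.** On its plain meaning the clause removes steps that are atypical for that child. The participants are aged 3 to 11 and the target is walking at a self-selected speed. A stumble or a run can be technically clean and pass both knee limits, so some such rule is defensible. Neutral removal does no harm in the check above, and the directional figures rest on a pattern that nothing in the documents shows to occur. The second threshold, SEM or MCID, gives some protection. All of this stands, and it limits the point to a risk that the plan leaves open.

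Three stronger readings are tempting and are not supported.

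- A reader might infer that trials are removed by eye after the outcome curves have been seen. Judging is described after the data are in Matlab, which makes this possible, but it is not written. Video or session notes would fit the text equally well.
- A reader might infer from the Procedure section that one person selects both the pre and the post trials. That sentence concerns who performs the assessments. Nobody is named for gait quality control, and keeping one assessor per child is an ordinary way to limit rater variation.
- A reader might infer that a gait control group would have cancelled the bias. Selection driven by an expected treatment effect would not cancel unless the person selecting trials were also masked to group. What can be said is that no comparison in the plan would expose it.

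What the objection does not remove is that the criterion is undefined, masking to visit is not stated, and the outcomes affected are primary.

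**Conclusion.** The concern holds as a gap in bias control. A subjective exclusion with no stated criterion and no stated masking acts on trials that feed the primary gait outcomes, and these are compared only pre versus post. Selection leaning in the expected direction could create or inflate a change. That it happens, or how large it would be, cannot be established from the documents: step counts, variability, the number of children with gait data and the SEM and MCID values are all missing. Under the assumed inputs the false change runs from 0 (neutral removal) to about 2.7 degrees (3 of 10 steps, opposite directions at the two visits, every child). These figures illustrate a range and are not estimates for this trial. The technical and varus-valgus exclusions are not in question. The change is worth making because it is cheap and the plan as written offers no equivalent safeguard.

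**What to change.** 1. Carry out trial quality control on files with the visit label and date removed, with pre and post files in random order.
2. Apply any exclusion for unrepresentative gait by one rule set in advance that is neutral in direction and works within each session, for example distance from that session's own median in either direction.
3. Report the number of cycles excluded per visit and the reason.
4. Repeat the primary gait analyses with all technically valid cycles (artefact, gap, marker and varus-valgus criteria only) as a sensitivity analysis.

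A band on walking speed should not be presented as a filter on something other than the outcome, because walking velocity is one of the primary spatial-temporal parameters. Deleting the clause outright is a trade-off: it would bring technically clean but atypical strides into the averages. The sensitivity analysis shows the effect of the clause without forcing that choice.

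Cost: a file-recoding step, one extra analysis and some repeated quality control. Inclusion runs from May 2019 to June 2022 and the protocol is dated May 10, 2022, so some trials may already have been processed.

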All data analyses will be carried out with MATLAB Software (The MathWorks, Natick, MA, USA, 2020b). The quality of the individual stretches will be checked using custom-made software. Stretch repetitions will be excluded in case of inconsistent stretch velocities, poor surface EMG data, out-of-plane movement or indications of insufficient participant relaxation (constant EMG activity of the antagonist).

In order to quantify the alteration in muscle tone after BoNT-A treatment, the average RMS-EMG expressed in millivolts, will be calculated as the square root of the area underneath the RMS-EMG time curve, divided by the duration of the time interval, during the high-velocity stretch. The interval will start 200 milliseconds prior to the time point where maximum stretch velocity will be reached and ended at the time corresponding to 90% of the full ROM. This value will be referred to as the muscle activation during a high-velocity stretch. All BoNT-A-induced changes will be compared to previous reported SEM or BoNT-A-induced values.

The average RMS-EMG expressed in millivolts during a high-velocity stretch will be used as the primary outcome to assess alterations in muscle tone. Additionally, the increase during the high-velocity stretch will be calculated by subtracting the muscle activation during a low-velocity stretch, which will be calculated following the same method. This value will be called the change in muscle activation and will be included as a secondary outcome.

4. Clinical examination

A standardized clinical examination including assessments of ROM, spasticity, selectivity and strength will be performed during the pre- and post-BoNT-A assessments of the intervention group and during the pre-assessment of the control group. These data will be used to describe and compare both groups at baseline. The maximal dorsiflexion angle and popliteal angle (unilateral) will be assessed by goniometry. The level of spasticity will be assessed by the modified Ashworth scale and modified Tardieu scale. Muscle strength will be assessed by manual muscle testing, and selectivity will be assessed by the Selective Control Assessment of the Lower Extremity. The evaluations of strength and selectivity will not be included in the current investigation.

5. Statistical Analysis

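### The written EMG processing steps do not, taken together, produce the primary muscle-tone outcome in millivolts: the squaring step is not stated and the square root is misplaced

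*Combined protocol and SAP*

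**What the plan says.** All of the relevant text is in the combined protocol and SAP, Assessments, section 3 (Spasticity assessment).

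- First filter: "The raw EMG signals will be filtered by a 6th order zero-phase Butterworth bandpass filter (20-500 Hz").
- Second filter: the RMS envelope, abbreviated RMS-EMG, "will be computed after application of a low-pass 30 Hz 6th order zero-phase Butter-worth filter".
- Summary value, over an interval in the high-velocity stretch: the "square root of the area underneath the RMS-EMG time curve, divided by the duration of the time interval", reported in millivolts.
- Status: "The average RMS-EMG expressed in millivolts during a high-velocity stretch will be used as the primary outcome to assess alterations in muscle tone". The secondary outcome is obtained by "subtracting the muscle activation during a low-velocity stretch, which will be calculated following the same method".
- Benchmark: "All BoNT-A-induced changes will be compared to previous reported SEM or BoNT-A-induced values".

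No squaring or rectification step is named anywhere in the section, and no EMG sampling rate is given. The assessment as a whole is referred to an earlier publication ("This method has been previously described"). It is planned in a subset of 14 children. Section 5 (Statistical Analysis) tests the pre/post change with a Wilcoxon signed rank test.

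**The concern.** A low-pass filter yields an envelope only when it acts on a squared or rectified signal. Applied to the band-passed EMG itself, a 30 Hz low-pass removes almost everything that the 20-500 Hz filter was set to keep. The text names the two filters in sequence and nothing between them.

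The averaging step raises a second problem. An RMS envelope is already in millivolts, so a further square root of its area is not. The two descriptions imply different curves, and the plan does not say which is meant.

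At stake is whether the primary tone outcome can be reproduced from the plan, and whether its values can be set beside published millivolt figures.

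**Working it through.** The plan gives no figure to reproduce here. Two checks were made.

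**1. What survives the two filters in the written order**

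Inputs from section 3: Butterworth band-pass 20-500 Hz and Butterworth low-pass 30 Hz, both 6th order and zero-phase. Assumed, because the plan does not state them: sampling rates of 1500 and 2000 Hz, the reading of the filter order, and the signal spectrum.

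A zero-phase (forward-backward) filter has amplitude gain |H(f)|². So:

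- gain of the band-pass alone: A₁(f) = |H_bp(f)|²
- gain of both filters: A(f) = |H_bp(f)|² × |H_lp(f)|²
- share of band-passed power retained, for spectrum S(f): Σ S·A² / Σ S·A₁²
- RMS ratio: the square root of that share

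The EMG-shaped spectra are S(f) = f²·h⁴ / [(f² + l²)(f² + h²)²], with corner frequencies l/h of 60/120, 40/100 and 30/60 Hz. RMS ratios at 1500 Hz:

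| Reading of the order | -3 dB band relative to peak (Hz) | Flat | 60/120 | 40/100 | 30/60 |
|---|---|---|---|---|---|
| 6 poles per pass, both filters | 20.2-29.5 | 0.108 | 0.132 | 0.184 | 0.290 |
| Order counted over both passes (low-pass 3 poles, band-pass 4 poles per pass) | 18.2-31.2 | 0.100 | 0.122 | 0.169 | 0.266 |
| Band-pass 12 poles, low-pass 6 poles per pass | 20.7-28.9 | 0.116 | 0.146 | 0.202 | 0.316 |

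At 2000 Hz no ratio moves by more than 0.002. The range is therefore about 0.10 to 0.32 in RMS, or 0.10² = 1% to 0.32² ≈ 10% in power. The passband depends almost entirely on the stated cut-offs and order. The RMS ratios also depend on the assumed spectra.

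In a simulation of 300 noise bursts (flat spectrum, 2000 Hz), the burst RMS relative to the band-passed RMS was 0.11 in the written order and 1.00 when the signal was squared before the low-pass. The between-repeat coefficient of variation was about 24% and 4% respectively. These two percentages are illustrative.

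**2. Units of the averaged value**

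The phrase about the square root can be read with the division by duration inside or outside the root:

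| Unit of the RMS-EMG curve | √(area / duration) | √(area) / duration |
|---|---|---|
| mV (a rooted envelope) | mV^½ | mV^½·s^-½ |
| mV² (a low-passed squared signal) | **mV** | mV·s^-½ |

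Only one of the four cells is in millivolts: a squared curve with the division inside the root. The name RMS-EMG points to the first row, and the stated unit to the second.

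Two consequences follow if another cell is used:

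- With a rooted curve and a second root, the value scales with the square root of amplitude. A true 50% fall appears as 1 - √0.5 = 0.29, or about 29%.
- With the division outside the root, a constant curve of height k over duration T gives √(kT)/T = √(k/T). The value then depends on how long the interval lasts, which differs between low- and high-velocity stretches.

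**The case against.** The strongest reply is that the text is terse, not wrong. An RMS envelope includes squaring by definition, the low-pass can be its averaging step, and the plan does not say which signal the low-pass acts on. The literal reading would also make the 20-500 Hz band pointless. The later square root, reported in millivolts, suggests that the curve is a squared signal. The method is cited to an earlier publication, which could not be consulted here. All of this stands, and it makes loose wording the likeliest cause.

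It does not close the point. If the intended curve is squared, it is not the RMS envelope that the text names. If it is the RMS envelope, the later root is one too many. Two competent analysts could repair the text differently and report different numbers.

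A second reply is that processing is identical before and after treatment. The signed rank test is unchanged by a constant multiplier, so low amplitude alone does not bias it. This also stands, provided the spectral shape is similar at both visits. It does not cover the loss of precision or the comparison with external values. Nor does it cover a second root, which is not a constant multiplier and can reorder the differences.

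A reader might also infer that the surviving 20-30 Hz band is mostly movement artefact. The documents give no figure for that, and stretch repetitions with poor EMG or out-of-plane movement are to be excluded.

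**Conclusion.** The point holds as a specification fault in a primary outcome. As written, the filter sequence and the averaging rule do not jointly yield a value in millivolts.

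Taken literally, the filters leave about 20-30 Hz and an RMS of about 10-32% of the band-passed RMS. If the earlier benchmark values came from the full 20-500 Hz band, which the documents do not confirm, changes in millivolts would be about 3 to 10 times too small beside them (1/0.32 ≈ 3.1; 1/0.10 = 10). Precision would also fall, in a subset of only 14 children.

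A reader might conclude that the actual processing is wrong or that the pre/post test is invalid. The documents support neither. They do not show the script, and a common scale factor largely cancels in the paired test. The harm is conditional on the text being implemented as it stands.

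**What to change.** Correct the filter sentence and the averaging sentence together. Adding a root to the first while leaving the second unchanged would apply it twice. State one sequence with a single root:

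1. Band-pass the raw EMG at 20-500 Hz.
2. Square it.
3. Apply the 30 Hz zero-phase low-pass to the squared signal.
4. Then either (a) average that curve over the interval (area divided by duration) and take the square root of the result, or (b) take the root to form the RMS-EMG envelope and average it over the interval without a second root.

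Options (a) and (b) are both in millivolts but are not equal: the root of a mean is at least as large as the mean of the roots. Choose the one that matches the processing behind the earlier SEM and BoNT-A-induced values used for comparison. Give the sampling rate, and say how the order is counted for a zero-phase filter. Apply the same rule to the low-velocity stretch. Check the script against the revised text before the pre/post analysis.

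Cost: two sentences and a code check, with a re-run only if the script follows the literal wording.

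### The written formula for the primary muscle-tone outcome takes a root of a curve that is already an RMS envelope, so it cannot give an average in millivolts

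*Combined protocol and SAP*

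**What the plan says.** All of this is in section 3 of the protocol (Spasticity assessment) unless stated otherwise.

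- **Signal.** After filtering, "The root mean square envelope of the EMG signal (RMS-EMG) will be computed".
- **Outcome.** The measure is named an average RMS-EMG, is given in mV, and "will be calculated as the square root of the area underneath the RMS-EMG time curve, divided by the duration of the time interval". No equation or brackets accompany the sentence.
- **Window.** "The interval will start 200 milliseconds prior to the time point where maximum stretch velocity will be reached", and it "ended at the time corresponding to 90% of the full ROM". Its length is therefore set by each stretch.
- **Role.** "The average RMS-EMG expressed in millivolts during a high-velocity stretch will be used as the primary outcome to assess alterations in muscle tone".
- **Secondary outcome.** The change in muscle activation is obtained by "subtracting the muscle activation during a low-velocity stretch, which will be calculated following the same method".
- **Stretches.** The slow ones are described as "Four low-velocity (during 5 seconds) passive stretches". The fast ones are done at maximum speed, with no duration given.
- **Benchmarks.** Changes are to be set against published SEM values or published treatment effects. The plan states neither the formula nor the unit behind those figures.
- **Source.** For the technique as a whole, "This method has been previously described" in earlier work that the plan cites.

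The assessment is made in a subset of 14 children. Section 5 (Statistical Analysis) tests the pre-post change with a Wilcoxon signed rank test at alpha 0.05.

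**The concern.** An RMS envelope is a voltage: its root has already been taken. The area under it is a voltage multiplied by a time. Dividing that area by the duration gives a mean voltage, and no further root is needed. The sentence nevertheless takes one, and does not show whether the division falls inside or outside it. The name and unit promise one quantity and the recipe delivers another.

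Three things are at stake. A named primary outcome cannot be reproduced from its own definition. The sizes reported for tone reduction would be on the wrong scale if the sentence were coded as it stands. The planned comparison with published values is one of size, so a rank test gives it no protection. The secondary outcome inherits the fault, because the slow stretch is handled in the same way.

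**Working it through.** The plan gives no numerical value to reproduce; the figure to test is the stated unit, mV. The unit result below needs no assumption. EMG amplitudes and fast-stretch windows are not in the documents, so those used here are illustrations.

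Let E(t) be the RMS-EMG envelope in mV, T the window length in s, and S the area under E(t) in mV·s.

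**1. Units.**

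| Formula | Unit | Written in the plan? |
|---|---|---|
| sqrt(S/T), division inside | mV^0.5 | possible reading |
| sqrt(S)/T, division outside | mV^0.5 s^-0.5 | possible reading |
| S/T | mV | no |
| sqrt(area under squared EMG / T) | mV | no |

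**2. Constant envelope, E = 0.02 mV (assumed).** S = 0.02·T. A correct average must return 0.02 at every T.

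- S/T = 0.02.
- Inside: sqrt(0.02) = 0.141.
- Outside, with T in seconds: sqrt(0.02 × 0.5)/0.5 = 0.200 at T = 0.5 s, and sqrt(0.02 × 0.3)/0.3 = 0.258 at T = 0.3 s.

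The two readings have different units, and the outside number depends on measuring T in seconds. I therefore quote no ratio between them.

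**3. Change of unit.** Writing the same signal in microvolts should multiply the outcome by 1000. Either reading is multiplied by sqrt(1000) = 31.6.

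**4. Compression at fixed T.** A true proportional fall f reads as 1 − sqrt(1 − f) under both readings: 30% reads as 1 − sqrt(0.7) = 16%, 50% as 1 − sqrt(0.5) = 29%, and 70% as 1 − sqrt(0.3) = 45%.

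**5. Window length, division outside only.** For constant amplitude a, sqrt(aT)/T = sqrt(a/T).

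- Same amplitude, window shortened from 0.5 to 0.4 s: sqrt(0.5/0.4) − 1 = +11.8%.
- Equal amplitude at both velocities: the high value exceeds the low value by the factor sqrt(T_low/T_high), which does not depend on the time unit. The true ratio is 1.

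For the 5 s stretch, T_low depends on the assumed velocity profile. A bell-shaped (minimum-jerk) profile gives 1.47 s. Constant speed reaches 90% of the range at 4.5 s, so a peak placed at 2.5 s gives 4.5 − 2.3 = 2.2 s, and one at 0.7 s gives 4.5 − 0.5 = 4.0 s. With assumed fast windows of 0.5, 0.4 and 0.3 s, the factors are sqrt(1.47/0.5) = 1.71, sqrt(2.2/0.4) = 2.35 and sqrt(4.0/0.3) = 3.65. The high-minus-low outcome is then not zero when activation is equal.

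**6. The two formulas that do give mV are different quantities.** For a flat envelope they agree (ratio 1). For a burst of height B filling fraction p of the window on a silent base, the mean is pB and the RMS is sqrt(p)·B, so RMS/mean = 1/sqrt(p): 1.41 at p = 0.5, 2.00 at p = 0.25, 3.16 at p = 0.10. There is no upper bound.

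**7. The planned test.** A simulation with n = 14, 2000 runs, lognormal amplitudes and no systematic pre-post shift in window length gave rejection rates of 4.3% to 5.2% under no effect for the plain average and both root readings. Power for a 30% fall was 76% (plain average), 80% (inside) and 70% (outside) with a within-child log SD of 0.3, and 37%, 39% and 37% with 0.5.

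**The case against.** The strongest reply is that a word has been lost. Squaring is part of computing any RMS. If the area meant is that under the squared signal, the root with the division inside gives mV. With the division outside, even a squared curve gives mV·s^-0.5. The stated unit therefore favours the inside reading, and the dependence on window length goes with the other one. That much stands, and it makes step 5 less likely to apply. It does not rescue the sentence: nothing in the plan squares the curve, and an average RMS-EMG is more naturally S/T, a different number. A colleague cannot pick one silently.

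The cited earlier work may hold the intended equation and the benchmark units. That is possible, but the plan writes out its own rule, and a reference to a method does not override it. If outcome and benchmarks do share a formula, the comparison is like for like whatever the label.

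It can also be said that little inferential harm follows. This largely stands. A square root preserves the direction of change between two values, and percentage change is not planned for the spasticity outcomes, so step 4 only shows the size of the distortion.

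A reader might infer more: that the spasticity data were processed wrongly, that the Wilcoxon test is invalid, or that the secondary outcome changes sign. The documents do not support these. The MATLAB code is not shown. Step 7 gives no sign of type I error inflation or a general loss of power. With the division inside, for a baseline low-to-high ratio of 0.3 to 0.2, reversal needs the low-velocity value to fall by more than 51% to 60% while the high-velocity value falls by 30%, or by more than 78% to 88% while it falls by 50%. That is a special case, not an expectation.

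**Conclusion.** The rule is wrong as written. Under neither reading does it produce the quantity and unit that the plan assigns to its primary muscle-tone outcome; this follows from the plan's own definition of RMS-EMG alone. The numerical sizes are conditional on literal coding and on assumed amplitudes and windows. On that basis, 0.02 mV returns 0.141 (inside), a 50% fall reads as 29% at fixed duration, and with the division outside the secondary outcome is not zero for equal activation.

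If the rule is coded literally, the reported sizes, the mV label and any comparison with published values in mV would be wrong. Harm to the type I error of the Wilcoxon test is not shown; the simulation assumed no systematic pre-post shift in window length. Reach is confined to the spasticity outcomes in the subset of 14; morphology and gait analyses are untouched. Severity is minor to moderate.

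**What to change.** Replace the sentence with one explicit equation that yields mV, and apply it at both velocities.

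- The equation that matches the stated label is the area under the RMS-EMG curve divided by the window duration.
- If a root is intended, write the square root of (area under the squared EMG curve divided by duration), and label it RMS over the window.

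Because the two are not interchangeable, name one without reference to the pre-post results. Confirm that the MATLAB script uses it, and rerun the script on the stored recordings if it does not. Check which formula and unit lie behind the benchmark SEM and treatment-effect values. If they rest on the root formula as now written, either report the outcome on that scale with its correct unit for that comparison, or do not compare the mV values with them.

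The cost is one equation, one unit label, a look at the cited sources, and a check or rerun on stored EMG data from 14 children. No new measurements are needed.
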